Protocol Title: Assessment of Investigational Positron Emission Tomography and Post-Processing Procedures Performed as add-ons to Standard of Care Imaging

Protocol Date: December 20, 2017

Research Project Number: RP0689

Principal Investigator: [name], PhD
Professor of Radiology and Novartis Chair of Imaging Research
Vice Chair of Research, Department of Radiology
[name]
[name]

[contact]

Office: [contact]
[contact]

I. Objectives

The purpose of this study is to utilize investigational Positron Emission Tomography (PET) imaging acquisitions in addition to standard of care imaging:

1. To develop and refine PET post-processing acquisition procedures.
2. To generate preliminary and comparative imaging data for potential clinical trials.
3. To retrospectively evaluate standard of care PET imaging acquisitions by comparison with investigational PET imaging acquisitions.

II. Background and Rationale

PET imaging is increasingly being used as a diagnostic modality in cancer detection, staging and response assessment. Additionally, PET imaging is utilized in the detection and assessment of neurodegenerative or neurofunctional diseases, cardiovascular diseases as well as inflammatory processes. Constant advances in imaging acquisition and post-processing approaches enable a large variability of acquisition settings that can only be evaluated in real clinical situations with comparison to current standard of care imaging. We are proposing in this research only to use modified PET acquisition and post-processing approaches that do not lead to any additional radiation exposure or other risks to the patient.

III. Procedures

A. Research Design

The ***prospective portion*** of this study will utilize investigational PET acquisitions in addition to standard of care PET imaging to develop and optimize PET acquisition post-processing techniques as well as to generate preliminary and comparative data for potential clinical trials. These post- processing techniques include but are not limited to visual inspection of lesions, normal tissue, sentinel nodes and imaging artifacts, semi-quantitative analysis including the use of rating schemes, and using various published methods for image post-processing. The PET methodologies we plan to use as part of this study will allow us to obtain morphological, functional and molecular information.

Patients receiving a standard of care PET will be asked by study personnel if they are interested in undergoing additional investigational acquisitions before or after their standard of care imaging. If the patient agrees, he/she will remain on the same PET scanner for up to an additional 30 minutes while more images are obtained. Each patient will be imaged for no longer than 2 hours (standard of care imaging and additional investigational imaging). A routine clinical report will be generated for the clinically indicated PET by a nuclear medicine physician. Once this routine clinical PET scan is dictated and finalized, a study team member will obtain the report via IHIS and manually remove all identifiers. This report is being obtained for comparative purposes. All the data being compared will be coded using a unique study number.

Patients will be asked to provide study personnel with authorization to their medical records for follow-up on future related procedures as well as the current outcome of their imaging procedure. Additionally, participants will be asked if their imaging data from this study can be

used in a de-identified manner in the future for comparison with other imaging data or as preliminary data for the protocol development of clinical trials.

The ***retrospective portion*** of this study will involve the review of pre-existing PET imaging data collected from January 1, 2001 through December 5, 2017. The data to be reviewed/analyzed includes PET imaging data that has been previously collected in the course of standard clinical care. The PET imaging acquisitions obtained from the retrospective review will be utilized as a comparison to the investigational images obtained during the prospective portion of this study. The criteria that will be utilized to determine how the retrospective data will be utilized includes the following parameters: type of imaging study, diagnosis, age in decades, gender, and availability of data in the imaging archive.

B. Sample

The ***prospective portion*** of the study population will include 200 evaluable patients receiving a standard of care PET scan at The Ohio State University (OSU). Potential participants will be identified by study team members at the time of the patient's standard of care imaging procedure.

Inclusion Criteria:

- Male and female volunteers greater than or equal to 18 years of age.
- Patients receiving a standard of care PET scan at OSU.

Exclusion Criteria:

- Participants who are pregnant or lactating.
- Prisoners.
- Subjects incapable of giving informed written consent.

The ***retrospective portion*** of the study population will include up to 500 evaluable previously acquired and archived standard of care PET scans. The selection of the cases will be based on availability of a data set and match in disease or age or gender to cases of the prospective population. All retrospective datasets will be de-identified using an established approach that is detailed below.

Inclusion Criteria:

- Patients having receiving a standard of care PET scan that is archived at OSU.

C. Measurement / Instrumentation

Studies will be carried out using FDA approved PET scanners. PET is routinely used for clinical diagnostic studies.

D. Detailed study procedures

In the ***prospective portion***, written informed consent will be obtained from each participant prior to any protocol related activities in a private area with a study team member. As part of this procedure, study personnel will approach eligible participants and explain verbally and in writing the nature, duration, and purpose of the study as well as all associated risks and benefits. They will inform the participant that he/she may withdraw from the study at any time.

The patient will be given time to ask questions and review the consent form on their own. During the consent process, the patient will be asked if he/she 1) is willing to provide a release of their medical records pertaining to future procedures/injuries in the next 10 years and 2) is willing to allow their de-identified data to be used as comparison data in other research studies or as preliminary data for the development of clinical trials. If the patient agrees, he/she will have additional PET acquisitions before or after their standard of care PET imaging. The patient will remain on the same PET scanner for all acquisitions. The investigational imaging will take no longer than 30 minutes. Each patient will be imaged for no longer than 2 hours (standard of care imaging and additional investigational imaging).

In the ***retrospective portion*** of the study, all PET/CT imaging data will be downloaded from the imaging PET Grid or archive system to the dedicated imaging corelab service where the imaging data will then be de-identified and referenced only by a study ID number. We will retain / code the following information regarding the data so that we may use it comparatively with matched investigational PET imaging data: type of imaging, diagnosis, coded imaging exam date, gender, age in decades, weight in 20 pound increments, and height in feet increments (i.e. excluding inches).

The date of the exam will be coded to the first day of the quarter when the study was performed, except in cases where follow up studies are performed at a shorter time interval. If a shorter time interval exists, the date will be coded in relation to the baseline study that will be coded as the 1st of the quarter. For example, a baseline CT scan was performed on 10/5/2017 with a follow up on 10/7/2017, and the date coding would be 10/1/2017 for the baseline and 10/3/2017, preserving the relative time ratio within the quarter, but changing the date to a coded date.

Image Collection:

All patients in the prospective portion of this study will receive a standard of care PET. Patients will be asked to simply lie on the table of the PET system for the duration of clinically indicated PET. Subjects participating in the additional investigational imaging sequence will be asked to lie on the table for an additional 30 minutes before or after standard of care imaging while acquisitions are obtained. Participants will not participate in more than a total of 2 hours of imaging time per day because they will become uncomfortable lying still in one position and motion compromises the image quality.

Release of Medical Records:

The patient will be asked if he/she is interested in releasing their medical records for up to 10 years after their participation in this study in order to allow study personnel to track the current outcome and/or related procedures in the future. The patient can revoke their consent to this question at any time by contacting the Principal Investigator

Additionally, patients will be asked if their de-identified data can be used for other research studies as comparative or preliminary data. The patient can change their response to this question at any time by contacting the Principal Investigator.

E. Risks, Benefits, Safety and Confidentiality:

The patient will be injected with a radiopharmaceutical for the standard of care PET imaging procedure. The patient will not receive any additional radiation from the investigational imaging acquisitions obtained.

Risks:

There are no additional safety risks associated with the investigational PET imaging.

Benefits:

It is hoped that the information from this study will initiate changes in the field of view, changes related to table movement and changes due to detector settings such as energy window.

Safety Monitoring:

As part of the standard of care imaging procedure, safety monitoring measures on the patients. This will include the monitoring of the physiologic parameters that are deemed appropriate in the evaluation of potential risk during the acquisition process (electrocardiogram, respiration rate, core body temperature). These parameters are monitored to ensure that they do not approach potentially hazardous levels. The Principal Investigators or Co-Investigators are able to respond immediately to ensure the safety of the patients participating in the research study. The Principal and/or Co-Investigators or Key Personnel will be present at the time of all PET acquisitions to ensure this.

Patient participation maximum duration and frequency is defined by protocol as follows: Duration of data acquisition in the PET system per patient is limited to no more than 2 hours total per day consisting of one or more acquisitions.

In the event of any medical emergency, accident or trauma while the subject is in the laboratory, our contingency plans for emergency situations are as they would be for any medical facility and clinical magnetic resonance imaging facility. Our emergency protocol fully prepares us to provide access to emergency treatment for our patients, resuscitation, life support and medical care as needed.

Confidentiality of Records:

All paper and electronic data/information will be de-identified prior to any review or analysis. All paper documents will be stored in a locked file cabinet with limited access in the Department of Radiology at The Ohio State University. All electronic data obtained through PACS or IHIS will be stored in a de-identified manner on password protected servers with limited access in the Department of Radiology at The Ohio State University. In the Informed Consent, we are asking subjects for release of medical records for up to ten years, as well as the use of de-identified data for other future studies. This data will become part of the permanent archive of the Wright Center of Innovation and may be kept indefinitely. No individual identities will be used in any publications resulting from this study. If the subject has authorized the use of de-identified data for other research studies as comparative data, the de-identified data may be shared with collaborative investigators as well as research databases. The established processes to verify de-identified data will always be adhered to. Officials from examining bodies such as the U.S. Food and Drug Administration or NIH may inspect records pertaining to this study.

F. Internal Validity

Image data will be evaluated following standard published procedures. This includes but is not limited to visual evaluation of lesions, normal tissue, sentinel nodes and imaging artifacts, semi-quantitative analysis including the use of rating schemes, and using various published methods for image post-processing. This should ensure internal and external validity of the data and avoid study bias. Functional and molecular read outs will be established according to methodologies.

G. Data Analysis

As the purpose of this data is to demonstrate feasibility in real life applications, we do not intend to perform a statistical assessment beyond classifying the characteristics of pilot data and comparing observational trends either to the standard of care imaging data or other known reference data. For our purposes, imaging that presents lower imaging quality will not be pursued for further evaluation. Only images that suggest equivalent or improved image quality would be evaluated for the potential use of preliminary data toward a formal Phase I/II clinical trial.

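### Section III.B accepts an archived comparator that matches on disease or age or gender, so gender alone admits practically every available scan, whatever its disease, kind of PET study or era

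*Protocol*

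**What the plan says.** Three parts of the protocol bear on how archived scans are chosen and used.

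- **III.B Sample, retrospective portion.** This is the only selection rule: "The selection of the cases will be based on availability of a data set and match in disease or age or gender", the match being to the prospective cases. The single inclusion criterion is "Patients having receiving a standard of care PET scan that is archived at OSU". The number is capped at 500.
- **III.A Research Design, retrospective portion.** The archived acquisitions come from a "review of pre-existing PET imaging data collected from January 1, 2001 through December 5, 2017" and "will be utilized as a comparison to the investigational images obtained during the prospective portion of this study". The parameters governing how they are used are "type of imaging study, diagnosis, age in decades, gender, and availability of data in the imaging archive".
- **III.D Detailed study procedures, retrospective portion.** Fields are kept so that the data can be compared with "matched investigational PET imaging data: type of imaging, diagnosis, coded imaging exam date, gender, age in decades", together with banded weight and height.

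On the prospective side, III.B enrols 200 evaluable patients, with the criterion "Male and female volunteers greater than or equal to 18 years of age". No disease restriction applies to either group.

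**The concern.** A comparator should resemble the case it is compared with in whatever drives the appearance of the image. The three characteristics in III.B are joined by *or*, so a scan that shares only the patient's gender is eligible. The kind of PET study, which III.A places first in its list, is absent from III.B. So is exam date, although III.D retains it in coded form. Archived patients may be under 18, while prospective patients may not.

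Objective 3 compares standard of care acquisitions with investigational ones, and III.A assigns the archived scans to that comparison. The Background names oncological, neurological, cardiovascular and inflammatory uses of PET and stresses continuing technical change. If comparators differ from the case in indication, kind of study or era, an apparent difference in image quality, or an apparent equivalence, may reflect those factors and not the investigational acquisition. III.G plans description only, with no adjustment, so case selection is the main safeguard for this comparison.

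**Working it through.** The protocol gives no figure for this point, so there is nothing to reproduce. The check takes the rule literally.

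**1. Whole prospective sample.** Once at least one man and one woman are enrolled, every available scan from a man or a woman matches some case on gender. With n = 200 (III.B) and an assumed share f for the less frequent sex:

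P(both sexes enrolled) = 1 − (1 − f)^200 − f^200

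| f (assumed) | P(both sexes enrolled) |
|---|---|
| 0.02 | 0.982 |
| 0.05 | 0.99996 |
| 0.10 or more | above 0.99999 |

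At this level the rule excludes practically nothing.

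**2. One prospective case.** Let g, a and d be the shares of the archive that match the case on gender, age decade and disease. The documents give none of these. I assume g = 0.5, a = 0.15 to 0.25, d = 0.05 to 0.30, and independence.

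- Share that qualifies: P = 1 − (1 − d)(1 − a)(1 − g)
- Same-disease share of qualifying scans: d / P
- Gender-only share of qualifying scans: (1 − d)(1 − a)g / P

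| d | a | P | Same disease | Different disease | Gender only |
|---|---|---|---|---|---|
| 0.05 | 0.15 | 1 − 0.95 × 0.85 × 0.5 = 0.596 | 0.084 | 0.916 | 0.677 |
| 0.05 | 0.25 | 1 − 0.95 × 0.75 × 0.5 = 0.644 | 0.078 | 0.922 | 0.553 |
| 0.30 | 0.15 | 1 − 0.70 × 0.85 × 0.5 = 0.703 | 0.427 | 0.573 | 0.423 |
| 0.30 | 0.25 | 1 − 0.70 × 0.75 × 0.5 = 0.738 | 0.407 | 0.593 | 0.356 |

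So 60% to 74% of the archive qualifies, 57% to 92% of qualifying scans have a different disease, and 36% to 68% match on gender only. Letting g run from 0.4 to 0.6 puts the same-disease share at 0.05/0.715 = 0.070 to 0.30/0.643 = 0.467, so 53% to 93% differ.

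**3. Without independence.** Every gender match qualifies, so P is at least g = 0.5, and the same-disease share is at most d/0.5 = 2d. That is 10% at d = 0.05 and 60% at d = 0.30. Mismatches are therefore the majority whenever d is below 0.25, whatever the dependence.

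**4. Fields named in each section.**

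| Field | III.A (use) | III.B (selection) | III.D (retained) |
|---|---|---|---|
| Type of imaging study | yes | no | yes |
| Diagnosis or disease | yes | yes | yes |
| Age | yes | yes | yes |
| Gender | yes | yes | yes |
| Exam date | no | no | yes, coded |

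None of the three says how many fields must agree.

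**5. Window.** 1 January 2001 to 5 December 2017 is 16.9 years, with no limit or preference on exam date inside it.

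**The case against.** The strongest reply is that selection and use are separate steps: III.B defines a broad pool, and III.A then governs use through a list that begins with type of study and diagnosis. That reading is coherent, and nothing says a case will be paired with a scan of another disease. But III.A lists parameters without requiring agreement on any of them, and III.D refers to matched data without a matching rule. No section turns the broad pool into a matched one.

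Second, the proportions rest on assumed shares, and the protocol does not say how finely disease is defined. This stands. If disease meant a broad class with an assumed share of 0.60, P would be 0.83 to 0.85 and only 28% to 29% of qualifying scans would differ. The illustration changes; the rule still admits a scan on gender alone.

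Third, the case-level rule does exclude 26% to 40% of the archive under the assumptions above, and all comparators are PET scans, so a different imaging type means a different kind of PET study. Both points are right.

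Fourth, matching detail could be left to an analysis plan. That would answer a silent protocol, but III.B states a rule, and it is the stated rule that is loose. The missing age floor and date preference contradict nothing by themselves; they are worth settling in the same edit.

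Last, the analysis is descriptive and a within-patient comparator exists: "The patient will remain on the same PET scanner for all acquisitions". This limits the consequence and is accepted.

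**Conclusion.** The concern holds. As written, III.B is close to non-restrictive across the prospective sample and permits comparators that differ from the case in disease, kind of PET study and era. That rests on the wording and on both sexes being enrolled. The case-level percentages rest on assumed match shares; they describe which scans are eligible, not which would be picked. The effect is limited to the descriptive archive comparison under Objective 3. The same-scanner, within-patient comparison is untouched. The change should be made, but the study does not fail without it.

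**What to change.** Replace the III.B rule with wording such as: *match on type of imaging study and diagnosis, and then on age decade and gender, among scans of patients aged 18 or older, preferring the nearest coded exam date.* Make III.A state the same rule.

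Three details should be settled in the same edit: how finely diagnosis is defined, whether age decade and gender are required or only preferred, and what happens to a case with no match. The age floor must be applied before age is coded in decades, because a decade band cannot separate 18 from 17. The archive window closes before the protocol's date of 20 December 2017, so the nearest exam will in practice be the most recent suitable one. Recording scanner model, where the archive holds it, is optional.

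The cost is protocol wording and a smaller eligible pool. As an illustration, if disease, age decade and gender all had to agree, the assumed shares give 0.5 × 0.15 × 0.05 = 0.4% to 0.5 × 0.25 × 0.30 = 3.8% of the archive per case, before type of study is added. Archive size is not stated, so the number left cannot be computed; this is a reason to treat age and gender as preferences if matches prove scarce. III.D already retains every matching field, and because 500 is a ceiling, no stated number would be missed.

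### Does coding archived exam dates to the quarter spoil the intervals between a patient's scans?

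*Protocol*

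**What the plan says.** The retrospective part draws on "pre-existing PET imaging data collected from January 1, 2001 through December 5, 2017" (Protocol III.A) and takes up to 500 archived scans (III.B). III.D sets out the date coding used in de-identification. The general rule is "The date of the exam will be coded to the first day of the quarter when the study was performed". It is qualified by "except in cases where follow up studies are performed at a shorter time interval", in which case the follow-up is dated from a baseline that is itself coded to the first of its quarter.

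One example is given: a baseline on 5 October 2017 with a follow-up on 7 October 2017, for which "the date coding would be 10/1/2017 for the baseline and 10/3/2017, preserving the relative time ratio within the quarter".

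The coded date is kept with type of imaging, diagnosis, gender and banded age, weight and height "so that we may use it comparatively with matched investigational PET imaging data". Under Confidentiality of Records (III.E), "All paper and electronic data/information will be de-identified prior to any review or analysis".

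**The concern.** Two things look wrong.

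First, the exception has no threshold. It could cover scans in the same calendar quarter, which the example and its wording suggest, or scans less than a quarter apart. Two people coding the same pair in good faith could record different intervals.

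Second, every pair outside the exception has its two dates rounded down by different amounts, so the coded interval is distorted and the order of two intervals can even be reversed. Because de-identification comes before review, whoever works with the data sees only the coded dates, with nothing to show which intervals are exact.

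At stake would be any description or grouping of archived scans by time since baseline. The apparent remedy is cheap: date every follow-up from its coded baseline, whatever the gap.

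**Working it through.** **Inputs.** The rule, the exception and the example come from III.D; the date window, 1 January 2001 to 5 December 2017, comes from III.A. That window holds 6,183 days.

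**Formulas.** Let q(d) be the first day of the quarter containing d, and offset(d) = d − q(d).
- General rule: coded interval = q(follow-up) − q(baseline), so error = offset(baseline) − offset(follow-up).
- Exception: coded follow-up = q(baseline) + true interval, so error = 0.

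**The protocol's example.** q(5 October 2017) = 1 October. Adding the true 2 days gives 3 October, as stated. Rounding both dates down would have given 0 days, which is what the exception prevents.

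**Bound.** The longest quarters have 92 days, so the largest offset is 91. A scan of all pairs up to 730 days apart gives errors from −91 to +91 under either reading of the exception:
- 31 March to 1 July 2017: 92 days true, 1 January to 1 July coded = 181.
- 1 January to 30 June 2017: 180 days true, 1 January to 1 April coded = 90. The order of these two intervals is reversed.

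**Two readings of one pair.** 20 September to 20 October 2017 is 30 days.
- Same-quarter reading: 1 July and 1 October, 92 days.
- Less-than-a-quarter reading: 1 July and 31 July, 30 days.

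On the same-quarter reading, a 30-day pair is miscoded if it crosses a quarter boundary. The window contains 67 boundaries, and 67 × 30 = 2,010 of 6,183 − 30 = 6,153 pairs cross one, or 32.7%. For 1-day pairs it is 67 of 6,182, or 1.1%.

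**Typical error when both dates are rounded down**

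| True interval (days) | Mean absolute error (days) |
|---|---|
| 92 | 1.4 |
| 120 | 39.3 |
| 135 | 45.6 |
| 150 | 41.9 |
| 180 | 5.1 |
| 225 | 45.4 |
| 365 | 0.5 |

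At 135 days, 3,165 of 6,048 pairs code as 90–92 days and 2,883 as 181–184, so no pair is less than 135 − 92 = 43 days off. If all pairs up to 730 days apart were equally likely (an assumption; the protocol gives no mix of intervals), the mean absolute error outside the exception would be about 30 days, and about 44% of pairs would be off by more than 30.

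**Where an interval would be used.**
- Objectives (I): developing acquisition and post-processing, generating preliminary data, and comparing standard with investigational acquisitions. None is longitudinal.
- Use and selection of archived cases (III.A, III.B): type of study, diagnosis or disease, age, gender and availability. Neither exam date nor spacing appears.
- Data Analysis (III.G): classifying pilot data and comparing observational trends. No interval is named.

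**What dating every follow-up from its baseline would do.** Interval error becomes 0, but follow-ups can leave their true quarter. For example, 30 September 2016 and 1 January 2017 (93 days) would become 1 July and 2 October 2016, so the follow-up lands in the wrong quarter and year. A 135-day follow-up would always be coded into the quarter after the baseline's, which is wrong for the 2,883 of 6,048 pairs (48%) that truly fall two quarters on. For 30-day pairs the share is the same 33% that cross a boundary. Under the general rule a coded date never leaves its true quarter.

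**The case for a change.** The best case for a change is that III.D itself lays down the coding rule, so this is not detail left to another document. The coded date is retained for comparison, and the exception shows that its authors cared about spacing. A rule that keeps 2 days exactly but can turn 92 into 181 then seems to miss its own aim, and one sentence would cure it.

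Part of this stands. The threshold is missing, the boundary case is ambiguous, and the errors between whole quarters are not small.

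The argument from intent goes too far, however. The stated aim is "preserving the relative time ratio within the quarter, but changing the date to a coded date", which is narrower than keeping spacing at every length. It stops close scans from collapsing onto one date. Beyond that the protocol chose quarter resolution, just as it bands age by decade, weight by 20 pounds and height by whole feet. A difference between two quarter-coded dates that is off by up to a quarter is what that resolution implies.

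Nor is the cure free. It would keep exact day counts of any length, up to nearly 17 years in this window, in data that III.E allows to be archived indefinitely and, where authorised, shared. It also gives up the correct calendar quarter.

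**Conclusion.** No change is needed. The calculation is sound: coded intervals outside the exception can be off by up to 91 days, with a mean of 39 to 46 days at the true intervals of 120, 135, 150 and 225 days and 5 days or less at 92, 180 and 365. But no result the protocol plans depends on those intervals, so a different rule would alter none of them. Coarse dates in exchange for stronger masking and an intact calendar quarter are a fair trade in a descriptive pilot comparison.

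The undefined term is a real but small gap in wording. The core lab can fill it by choosing one reading, applying it to every multi-scan patient and recording the choice. Anyone using the coded dates should treat longer intervals as known only to about a quarter.

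This rests on two things: that archived scans are used as the protocol describes, as matched comparators and not as patient time courses; and that nothing outside this document plans an analysis by time since baseline. The protocol does not say how many of the 500 scans are repeat scans or how far apart they lie, so the number of affected pairs cannot be estimated. If timing between scans were to become an outcome, the coding rule would need to be looked at again.

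### Does the III.F assurance on study bias leave the III.G image-quality judgement open to reader bias?

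*Protocol*

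**What the plan says.** Protocol III.F (Internal Validity) opens with "Image data will be evaluated following standard published procedures". It then gives an open-ended list: visual assessment, semi-quantitative analysis that includes rating schemes, and published post-processing methods. Its conclusion is "This should ensure internal and external validity of the data and avoid study bias". No procedure, scale or reference is named.

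Protocol III.G (Data Analysis) limits the analysis to describing pilot data and comparing observed trends with standard of care or other reference data. It then sets a filter: "For our purposes, imaging that presents lower imaging quality will not be pursued for further evaluation". The positive side of the filter is "Only images that suggest equivalent or improved image quality would be evaluated for the potential use of preliminary data", with a formal Phase I/II trial as the eventual use.

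Three other statements bear on the comparison:

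- III.A, on coding: "All the data being compared will be coded using a unique study number".
- III.E (Confidentiality of Records), on de-identification: "All paper and electronic data/information will be de-identified prior to any review or analysis".
- III.A, on the routine clinical report: "This report is being obtained for comparative purposes". It does not say which comparison the report serves.

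III.A and III.D also keep each prospective patient on one scanner for both the standard of care and the investigational acquisitions.

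**The concern.** Visual evaluation and rating schemes depend on a reader. The terms in III.G (lower, equivalent, improved) are comparative, and a reader who knows which image is the new acquisition may lean one way without meaning to. Citing published procedures in general does not show that this is prevented. III.F nevertheless presents bias as dealt with, so the complaint is about a positive statement and not only about missing detail.

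What is at stake is the III.G filter. If readers favour the investigational images, weak settings are carried forward. If readers are sceptical, useful settings are dropped. Either way, the retained set is selected on the judgement that may be biased.

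**Working it through.** There is no figure to reproduce. The protocol gives no quality scale, number of readers, margin, error rate or power for this judgement. The check is therefore textual: take each statement that could support the III.F assurance and ask what it controls.

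| Statement | Where | What it controls | Hides acquisition type from the reader? |
|---|---|---|---|
| Published evaluation procedures | III.F | Depends on the procedure, which is not named | Not known |
| Coding by study number | III.A | Patient identity in the compared data | Not stated |
| De-identification before review | III.E, Confidentiality | Patient identity | Not stated |
| Same patient, same scanner | III.A, III.D | Differences between patients and between scanners | No |
| Clinical report obtained only once final | III.A | Independence of the clinical report | No; the report is not described as a quality rating |

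**What the table shows.** The protocol has real protection for internal validity in the prospective part: the within-patient, same-scanner comparison removes the largest sources of difference unrelated to the acquisition. It has no stated protection against reader knowledge of acquisition type. The first row could supply it, because a published procedure may fix a scale or require masking, but the document does not allow that to be checked.

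**What the judgement decides.** The III.G filter applies to acquired investigational images. It is not the only selection in the study: III.B also selects up to 500 archived scans, by availability and by a match on disease, age or gender. Nor does III.G say that quality is judged by eye alone, or against the clinical report.

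**Consequence in each direction.** An acquisition wrongly kept is considered as preliminary data toward a formal Phase I/II trial, where it can be tested. An acquisition wrongly dropped is a lost lead, but its images remain and can be read again. Neither error feeds a test or an interval, because III.G plans none.

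**Cost of a masked paired reading.** With 200 patients and *k* investigational sets per patient, reads = 200 × (1 + *k*). At an assumed 5 to 10 minutes per read:

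| *k* (assumed) | Reads | Hours at 5 min | Hours at 10 min |
|---|---|---|---|
| 1 | 200 × 2 = 400 | 400 × 5 / 60 = 33.3 | 400 × 10 / 60 = 66.7 |
| 2 | 200 × 3 = 600 | 600 × 5 / 60 = 50 | 600 × 10 / 60 = 100 |
| 3 | 200 × 4 = 800 | 800 × 5 / 60 = 66.7 | 800 × 10 / 60 = 133.3 |

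The protocol gives neither *k* nor the reading time. It speaks of acquisitions in the plural, so 400 is a floor. The optional archived scans are not counted.

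**What that effort would buy.** III.E (Benefits) describes what may be varied: "changes in the field of view, changes related to table movement and changes due to detector settings such as energy window". Images that differ in these ways may be recognisable with the label removed, so masking may be only partial. One reader who sees both sets may also remember the patient, so the two reads would have to be kept apart in time. That gives up the side-by-side comparison, which has its own merit when acquisition settings are being developed.

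**The case for a change.** The strongest case for acting is that III.F does more than leave a detail for later: it draws a conclusion its stated basis cannot carry. No other section supplies the missing support. The protocol also shows that evaluation procedures cannot cover every source of bias. III.D notes that discomfort and motion degrade images, yet it allows the investigational acquisition on either side of the standard one without a rule for the order. Qualifying one sentence, or citing a reading manual, would cost almost nothing.

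Much of this stands. The sentence is generic, and on the text alone it does not show that reader bias is controlled. But it is worded as an expectation, not a guarantee, and it sits in a section on internal validity, to which the same-scanner design does contribute. The case for acting must also grant that citing an existing reading manual would settle the matter. That makes it a question of where reading rules are written down, and a protocol commonly leaves those to a document that is not at hand here. Masked reads in separate sessions versus side-by-side comparison is a choice on which experienced reviewers differ. The point on acquisition order concerns how images are acquired and does not show that the quality reading itself goes wrong.

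**Conclusion.** No change to the plan follows. III.F contains an optimistic sentence whose basis is not spelled out, and the protocol does not say whether the reader behind the III.G filter knows the acquisition type. This is a gap that the imaging team can fill sensibly in its reading procedure. It is not a rule that produces a wrong result.

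The judgement covers 200 prospective patients, at least 400 image sets if each has one or more investigational sets. No effect size can be derived, and there is no formal inference for a bias to distort. The consequence is limited to which acquisitions are considered as preliminary data for a later trial.

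The conclusion rests on three assumptions: that the analysis stays descriptive, as III.G says; that stored images remain available for re-reading; and that reading rules may be set in a document not shown here. If the retained images were used for a formal claim of equivalent or better quality, the reading conditions would have to be stated and the question would need to be reopened.
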